##### 3. Progression to steroid dependent nephrotic syndrome

- Definition (according to KDIGO criteria): two consecutive relapses during corticosteroid therapy, or within 14 days of ceasing therapy
- Timing: censored at 24 months
- Measurement value: number of patients (%)

##### 4. Cumulative dosage of prednisolone

- Definition: cumulative dosage of prednisolone during study period after the final prednisolone dose

- Timing: censored at 12 and 24 months
- Measurement value: mg/m^2

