### **Randomisation**

After prednisolone 60 mg/m^2 daily in 1 dose until complete remission for 3 days, randomisation (allocation ratio 1:1) between:

- Standard treatment: 6 weeks prednisolone 40 mg/m^2 (max. 40 mg) every other day;

- Study treatment: 2 weeks prednisolone 40 mg/m^2 (max. 40 mg) every other day, then 4 weeks placebo every other day.

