### **Blinding**

All researchers involved in the preparation of the analysis plan don't have access to trial data broken down by treatment allocation. Once data quality checks are satisfactory and the database is locked, a blind review will be undertaken to quantify missing data of the entire dataset and allow for any final amendments to the statistical analysis plan. During interim analysis and interpretation, group allocation will be masked using dummy group names (for example, group A, group B). The true group allocation will be unmasked only if necessary and after the database is locked. In addition, due to a difference of 4 weeks between the standard treatment and placebo group regarding timing of final prednisolone dose, time to first relapse and thereby all final statistical analyses can only be determined after unblinding. The randomisation list remains preserved by the hospital trial pharmacy and will not be accessible to the investigators until the end of the follow-up of the last patient. An unblinding procedure at the hospital pharmacy department will be available at all times.

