## ANALYSIS

### Outcome definitions

#### Primary outcome

##### Time to first relapse

- Definition: time to first relapse (=first day of treatment of the next relapse) after the final prednisolone dose. The final prednisolone dose represents the beginning of study medication for the placebo group and the end of study medication for the prednisolone group.
- Timing: censored at 12 and 24 months
- Measurement value: days

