##### Cumulative dosage of prednisolone during study period

- Depending on the distribution of the data, this will be analyzed with either the *t* test or the Mann-Whitney test.

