### **Interim analysis**

The total inclusion of 144 patients is expected to be finalized in 1.5 years, thereby the DSMB meeting will take place approximately 8 months after the start of inclusion. The mean follow-up period of the 40 patients at that time will be 5.5 (range 3-8) months. Previous literature shows a cumulative incidence rate of a first relapse of 30% after 5.5 months.[3] As the placebo group will receive approximately 35% less prednisolone during the study period, we based the power calculation on a difference of maximum 1/3rd earlier until the first relapse after study medication. Therefore we would like to advise the DSMB to check whether the patients with a relapse are in group A or B (dummy groups) if over 8 patients have experienced a relapse at interim analysis. Aim is then to check for a significant difference in relapse rate between the two groups. If there seems to be a significant difference between the two groups and the percentage of patients with a relapse in either one or both groups exceeds 40% than they might consider to unblind the groups.

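### Secondary outcome 4 counts prednisolone only after the final scheduled dose, so it cannot show the steroid spared by the shorter course

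*SAP*

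**What the plan says.** The Randomisation section allocates children, once in remission on daily prednisolone, to one of two schedules:

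- standard: "6 weeks prednisolone 40 mg/m 2 (max. 40 mg) every other day";
- study: "2 weeks prednisolone 40 mg/m 2 (max. 40 mg) every other day, then 4 weeks placebo every other day".

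Secondary outcome 4 is "cumulative dosage of prednisolone during study period after the final prednisolone dose", in mg/m², censored at 12 and 24 months. The starting point of that count is explained under the primary outcome: "The final prednisolone dose represents the beginning of study medication for the placebo group and the end of study medication for the prednisolone group". The Blinding section gives the size of the gap: "due to a difference of 4 weeks between the standard treatment and placebo group regarding timing of final prednisolone dose".

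Two other places bear on the point. The analysis section titles the same outcome "Cumulative dosage of prednisolone during study period", without the restriction to the time after the last dose. The Interim analysis section remarks, "As the placebo group will receive approximately 35% less prednisolone during the study period".

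**The concern.** The two arms are planned to differ in one thing only: four weeks of alternate-day prednisolone against four weeks of placebo. The counting window for cumulative dose opens after those four weeks in the standard arm and before them in the placebo arm. In the standard arm the active doses fall outside the window. In the placebo arm the same weeks fall inside it but hold no active drug. What remains is prednisolone given later, mainly for subsequent relapses.

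The Introduction gives the rationale as limiting the harm of the disease and of its treatment. A reader of the results will want to know whether the steroid spared at the start is still spared after later relapses are treated. As defined, the outcome cannot answer that, and its sign can differ from the sign of the difference in total exposure.

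**Working it through.** **Inputs**

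- Alternate-day dose: 40 mg/m², maximum 40 mg (SAP, Randomisation).
- Alternate-day phase: 6 weeks standard, 2 weeks study (same section).
- Daily phase before randomisation: 60 mg/m² per day, the same in both arms. Its length, D days, is not given; 7 to 21 days is assumed here.
- Stated saving: about 35% (SAP, Interim analysis).

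**Dose left out, below the 40 mg cap**

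- Standard arm: 42 days / 2 = 21 doses; 21 × 40 = 840 mg/m².
- Study arm: 14 days / 2 = 7 doses; 7 × 40 = 280 mg/m².
- Difference: 840 − 280 = 14 × 40 = 560 mg/m², or 560/840 = 66.7% of the standard alternate-day phase.

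The cap binds above 40/40 = 1 m² of body surface. At 1.5 m², for illustration, a dose is 40/1.5 = 26.7 mg/m² and the omitted amount is 14 × 26.7 ≈ 373 mg/m². So 560 is the maximum, under full adherence.

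**The plan's own 35%**

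Reduction over the index course = 560 / (60 × D + 840).

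| D (days, assumed) | Standard course (mg/m²) | Reduction |
|---|---|---|
| 7 | 1260 | 44% |
| 10 | 1440 | 39% |
| 12 | 1560 | 35.9% |
| 13 | 1620 | 34.6% |
| 14 | 1680 | 33% |
| 21 | 2100 | 27% |

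The 35% is met at D = (560/0.35 − 840)/60 = 12.7 days. Because the SAP does not give D, the figure is plausible but cannot be reproduced from the document. It fits a single treatment course that includes the daily phase.

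**What the outcome would show**

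Under the present definition the index course contributes 0 mg/m² in both arms.

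- Equal later steroid use: the outcome shows a difference of 0. Counted from randomisation, the difference is 560 mg/m² in favour of the reduced arm.
- More relapses in the reduced arm: suppose each later relapse is treated with a full standard course of C = 60 × D + 840. The saving is cancelled when the excess of relapses per child reaches 560/C, which is 560/1260 = 0.44 at D = 7 and 560/2100 = 0.27 at D = 21. Below that excess, the present outcome shows more steroid in the reduced arm while its total is lower.

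An example with C = 1600 (D = 12.7) and means of 1.0 and 1.2 later courses per child:

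| | Standard | Reduced | Reduced − standard |
|---|---|---|---|
| After the final dose only | 1600 | 1920 | +320 |
| From randomisation | 840 + 1600 = 2440 | 280 + 1920 = 2200 | −240 |

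**Other outcomes**

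None of the other listed outcomes (time to first relapse, number of relapses, progression to frequent relapsing or steroid dependent disease) measures dose. Table 1 shows self-reported dose by arm for weeks 1 to 4 only, as an adherence table.

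**The case against.** The strongest case for the plan is that the chosen window is deliberate and coherent. The primary outcome and the relapse count use the same starting point. The question it answers, whether a shorter course leads to more steroid later, is a proper one. The omitted dose is largely fixed by design, so adding it gives the reduced arm a known advantage. This stands in part: it is a reason to keep the post-course count, but not a reason to leave out the total, since no other outcome supplies it.

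A reader might infer that the SAP contradicts itself, because the title in the analysis section drops the restriction and the Interim analysis section speaks of 35% less over the study period. The document does not clearly support that. The title may be only a shortened name, and the definition uses the same study-period phrase itself. The 35% supports the assumed effect on time to relapse and does not define this outcome. The wording should be aligned, but a firm contradiction is not shown.

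A reader might also infer that the spared dose would be invisible in the report. Table 1 would show it in part, though without a 12- or 24-month total.

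The size also needs care. A break-even of 0.35 courses, taken from a course of 560/0.35 = 1600 mg/m², merely returns the SAP's 35%. Only the range of 0.27 to 0.44 is informative, and it rests on assumptions.

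**Conclusion.** The point holds as a gap in one secondary outcome. Its definition removes the only planned difference in exposure, up to 560 mg/m² per child below the 40 mg cap and less above it. It can therefore show no difference, or more steroid in the reduced arm, when total exposure is lower there.

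The exclusion and the 560 mg/m² follow from the SAP's own schedule, given full adherence. The break-even of about 0.27 to 0.44 relapse courses per child needs two things that the SAP does not state: a daily phase of 7 to 21 days, and full-course treatment of every later relapse. It is an illustration for children below the cap.

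It would go too far to call the outcome invalid or misleading in itself. Reported strictly as dose after the final dose, it makes no claim about total exposure. The primary conclusion is not affected.

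**What to change.** Redefine secondary outcome 4 as all prednisolone taken from randomisation to 12 and 24 months, with the same start date in both arms and with the blinded study medication included after unblinding. Keep prednisolone given after the final dose as a separately reported component, so that relapse-driven use stays visible. Use the same wording in the outcome definition and in the title in the analysis section.

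A common start date also settles a smaller matter. The present windows open about four weeks apart, and the SAP does not say whether the 12- and 24-month limits run from a common date or from each arm's final dose.

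The cost is mainly SAP wording. Study medication is already recorded by diary and returned medication (SAP, Adherence and protocol deviations), allocation is known after unblinding, and later doses are needed for the existing outcome. The SAP does not say that all prednisolone is recorded from randomisation onward, so the sponsor should confirm this, in particular for the two active weeks common to both arms. No treatment rule changes.

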### **Analysis methods**

#### Primary endpoint

##### Time to first relapse after the final prednisolone dose

- As normal distribution is not assumed, the median time to relapse will be compared between the groups using a Mann-Whitney test;
- In case patients did not experience any relapse after 24 months or patients are lost to follow up before they experienced a relapse, incidence rates or person-time rates will be used to compare the groups;
- If a normal distribution is shown in the Shapiro-Wilk W test, a *t* test will be used;
- The percentages of study subjects with a relapse at 12 and 24 months will be compared between the groups;
- The cumulative probability on the absence of a relapse will be estimated by survival analysis, according to the Kaplan-Meier method. Log-rank tests are used for the comparison between the standard treatment group and placebo group;
- To test for the influence of factors, such as the use of maintenance immunosuppressive therapy, logistic regression analysis for nephrotic syndrome relapses with covariate analysis will be performed;
- Within each subject time to relapse after study medication will be compared to time to relapse before entering the study using a paired sample *t* test. This test will exclusively be performed in patients without changes in maintenance therapy.

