### **Sample size**

From previous studies, we know the incidence of nephrotic syndrome in Dutch children to be 1.52/100,000 children/year.[2] Eighty percent of the pediatric patients develop at least 1 relapse of whom 50% continue towards frequent relapsing nephrotic syndrome. Based on data from previous studies, average time to relapse in the first year is approximately 185 days (standard deviation of 120 days).[3] Using the power calculation for a noninferiority trial with a continuous primary outcome, a power of 80% and a noninferiority limit of 50 days, 72 patients per group are required. Using a Cox Proportional Hazard time-to-relapse analysis (survival analysis)[4], similar numbers can be calculated.

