## **STATISTICAL PRINCIPLES**

### **Level of confidence intervals and p-values**

For this noninferiority trial, the upper bound of the 2-sided 95% confidence interval for the treatment effect has to be below the margin to declare that noninferiority has been shown. P-values <0.05 will be considered statistically significant.

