### Baseline patient characteristics

Discrete variables will be demonstrated by frequencies and percentages. Continuously distributed variables will be demonstrated using either mean  $\pm$  standard deviation for data with normal distribution, or median and interquartile range for non-normally distributed data.

Table 2: Participant baseline characteristics

	Standard treatment (n = xxx)	Placebo (n = xxx)
Participant characteristics		
Male, n (%)	n/N (%)	n/N (%)
Age, years; median (IQR)	xx.x (xx.x to xx.x), n	xx.x (xx.x to xx.x), n
Age at onset, years; median (IQR)	xx.x (xx.x to xx.x), n	xx.x (xx.x to xx.x), n
Descent, n (%)	n/N (%)	n/N (%)

- Caucasian - Asian - African - Other, specify		
Maintenance therapy, n (%) - Levamisole - Cyclosporine - Tacrolimus - Mycophenolate mofetil - Mycophenolate sodium - Prednisolone	n/N (%)	n/N (%)
Total number of relapses prior to study participation	n/N (%)	n/N (%)
Number of relapses in preceding 24 months	n/N (%)	n/N (%)

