#### Secondary endpoints

##### Number of relapses after the final prednisolone dose

- Follow-up will be categorized into three periods (period 1, 0-12 months, period 2, 12-24 months, period 3, 0-24 months) and within each period, the number of relapses is counted;
- Poisson regression will be used to evaluate relapse rates in relation to treatment, maintenance immunosuppressive treatment, sex, age and period.

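### Every between-arm comparison of time to first relapse is unadjusted; prespecified adjustment for relapse count, maintenance therapy and age could make the comparison in days more precise, by an amount the SAP does not determine

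*SAP*

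**What the plan says.** All references are to the SAP.

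- **Primary endpoint, Analysis methods.** The arms are compared in five ways. First, "the median time to relapse will be compared between the groups using a Mann-Whitney test". A t test replaces it if the data look normal. Person-time or incidence rates are used where children have not relapsed or are lost. The percentages relapsed at 12 and 24 months are compared. For the Kaplan-Meier curves, "Log-rank tests are used for the comparison between the standard treatment group and placebo group". No covariate or stratum is named for any of these.
- **Other uses of covariates in the same section.** A logistic regression examines whether factors such as maintenance therapy influence relapse. Separately, a before-after t test is planned: "Within each subject time to relapse after study medication will be compared to time to relapse before entering the study using a paired sample". It is restricted to children whose maintenance therapy did not change.
- **Baseline patient characteristics, Table 2.** The rows include age, maintenance therapy, total prior relapses and "Number of relapses in preceding 24 months". Previous time to relapse is not a row.
- **Secondary endpoint, number of relapses.** "Poisson regression will be used to evaluate relapse rates in relation to treatment, maintenance immunosuppressive treatment, sex, age and period".
- **Decision rule, Level of confidence intervals and p-values.** For noninferiority, "the upper bound of the 2-sided 95% confidence interval for the treatment effect has to be below the margin".

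**The concern.** Entrants range from children without maintenance therapy to children relapsing while on immunosuppressants. Some of the spread in days to relapse may therefore be predictable at entry. The SAP appears to share this view: the influence of maintenance therapy is a secondary objective, and the Poisson model for relapse counts includes maintenance therapy, sex and age. Yet nothing known at entry is used when the arms are compared on the primary endpoint.

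What is at stake is precision. In a noninferiority trial the width of the confidence interval decides whether a schedule that is truly no worse can be shown to be so. Variance that baseline covariates could explain, if left in the error term, widens the interval and makes an inconclusive result more likely. The logistic regression does not fill this gap. It models relapse yes or no, names neither a treatment term nor relapse history, and gives no effect in days to set against a limit stated in days.

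**Working it through.** **Inputs**

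- Sample size section: "average time to relapse in the first year is approximately 185 days (standard deviation of 120 days"), and "a power of 80% and a noninferiority limit of 50 days, 72 patients per group are required". No significance level is given there.
- Decision rule: two-sided 95% confidence interval, so z = 1.960.
- Assumed: true difference 0; rho, the joint correlation of the covariates with the outcome, from 0.2 to 0.5. The SAP gives no value for rho.

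**Step 1: reproduce the SAP's figure.** n per group = 2 × [SD × (z_alpha + z_0.80) / limit]².

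- One-sided 5%: 2 × [120 × (1.645 + 0.842) / 50]² = 71.2, rounded up to **72**. The stated figure is reproduced.
- One-sided 2.5%, which matches the two-sided 95% interval: 2 × [120 × (1.960 + 0.842) / 50]² = 90.4, rounded up to **91**.

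**Step 2: unadjusted power with 72 per group.** The standard error of the difference is 120 × √(2/72) = 20 days, and 50/20 = 2.5. Power = Φ(2.5 − 1.960) = **70.5%**. At one-sided 5% it is Φ(2.5 − 1.645) = 80.4%.

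**Step 3: power after adjustment on the days scale.** Linear adjustment replaces the SD by 120 × √(1 − rho²). Power = Φ(2.5 / √(1 − rho²) − z), and the equivalent unadjusted size per group is 72 / (1 − rho²).

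| rho | Residual SD (days) | Power, two-sided 95% CI | Power, one-sided 5% | Equivalent n per group |
|---|---|---|---|---|
| 0 | 120.0 | 70.5% | 80.4% | 72 |
| 0.2 | 117.6 | 72.3% | 81.8% | 75.0 |
| 0.3 | 114.5 | 74.6% | 83.5% | 79.1 |
| 0.4 | 110.0 | 77.9% | 86.1% | 85.7 |
| 0.5 | 103.9 | 82.3% | 89.3% | 96.0 |

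Under the two-sided 95% rule the gain is 1.8 points at rho 0.2 and 11.8 points at rho 0.5. Power returns to 80% at rho = √(1 − 72/90.4) ≈ 0.45.

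**Step 4: does the gain carry over to a hazard ratio?** The Sample size section mentions a Cox analysis, so this was checked by simulation: 400 trials per setting, 72 per group, true hazard ratio 1, an assumed margin of 185/135 = 1.37, and one covariate (log of the previous interval) of increasing predictive strength. Power was 45.8%, 48.0%, 46.5% and 42.5% unadjusted, against 46.8%, 47.5%, 47.5% and 41.8% adjusted. These agree within simulation error, so the benefit in Step 3 belongs to the days scale.

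**The case against.** **An unadjusted randomised comparison is valid.** This stands. Chance imbalance between arms is not bias, because the confidence interval already allows for it. The point is about efficiency.

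**The power figures describe an analysis the SAP barely contains.** They assume a difference in mean days. Of the listed methods only the conditional t test matches, and the SAP says normality is not assumed. It also does not say which estimate produces the interval to be set against 50 days. This stands as a limit on the figures. The missing estimator is a separate issue that must be settled at the same time. If it were settled by a Cox model, Step 4 suggests that adjustment would bring little.

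**The size rests on an assumed correlation.** This stands. One could try to derive rho by simulating children who differ in relapse rate, but the answer depends on how much they differ. Such a model also assumes one constant rate per child before and after entry, which a change in maintenance therapy would break.

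**Covariates are not ignored altogether.** True of the logistic and Poisson models, but neither gives an adjusted treatment effect in days.

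A reader might infer two stronger claims:

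- *The trial throws away power it could have for nothing.* The SAP does not support this. The gain may be under 2 points, and a rule for missing covariates would be needed.
- *Each child's previous time to relapse is on hand as a baseline value of the outcome.* The SAP does not show this. That interval is not in Table 2, and its one planned use is restricted to children without changes in maintenance therapy.

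**Conclusion.** The point holds as a worthwhile improvement, not as an error. All between-arm comparisons of time to first relapse are crude, although the relapse count, age and maintenance therapy are to be recorded at baseline and are plausible predictors.

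On the days scale, with SD 120, 72 per group, true difference 0 and the two-sided 95% interval, adjustment would raise power from 70.5% to between 72.3% and 82.3% for rho between 0.2 and 0.5. The documents do not say where in that range the trial lies. The calculation also treats days to relapse as fully observed with the stated SD; censoring and the chosen horizon would change the figures. The 70.5% starting point, rather than 80%, comes from the mismatch between the level behind 72 per group and the interval in the decision rule. That is a separate matter, though it makes any gain in precision more useful.

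**What to change.** Before unblinding, amend Analysis methods for the primary endpoint as follows. The Blinding section already allows final SAP amendments at blind review.

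1. State that the between-arm estimate in days set against the 50-day limit is adjusted for log(1 + relapses in the preceding 24 months), maintenance therapy at randomisation (yes/no) and age, and is reported with its two-sided 95% confidence interval.
2. Name a method that handles censoring, for example regression on pseudo-values for mean relapse-free days up to a stated horizon, or analysis of covariance with censoring weights.
3. Keep the unadjusted estimate as a sensitivity analysis.
4. Add previous time to relapse only if it is recorded for nearly all children, and decide this without reference to treatment allocation.
5. Give a simple fill rule for missing baseline covariates, as a stated exception to the Missing data section, which imputes nothing. Otherwise children with a missing covariate would drop out of the adjusted analysis.

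The cost is a few degrees of freedom out of 144 children, the fill rule, and possibly an analysis step beyond the standard SPSS menus. The three core covariates need no new data and no more patients.

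### The SAP's noninferiority rule needs a treatment effect with a 95% confidence interval to set against 50 days, but no listed primary analysis is planned to produce one

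*SAP*

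**What the plan says.** The trial is described as a noninferiority study (SAP, Trial design). The sample size was set "Using the power calculation for a noninferiority trial with a continuous primary outcome", and with "a power of 80% and a noninferiority limit of 50 days, 72 patients per group are required". The planning mean is 185 days and the SD 120 days, both for the first year.

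The decision rule (SAP, Level of confidence intervals and p-values) is that "the upper bound of the 2-sided 95% confidence interval for the treatment effect has to be below the margin". It does not name the effect measure, its unit or the direction of subtraction.

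The primary outcome is measured in days and "censored at 12 and 24 months", with neither horizon named as primary (SAP, Outcome definitions).

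The between-group comparisons in SAP, Analysis methods, Primary endpoint, are:

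- By default, "the median time to relapse will be compared between the groups using a Mann-Whitney test".
- "If a normal distribution is shown in the Shapiro-Wilk W test", a t test is used.
- If any child is relapse-free at 24 months, or is lost before relapsing, "incidence rates or person-time rates will be used to compare the groups".
- Percentages relapsing at 12 and 24 months are compared.
- Kaplan-Meier curves are estimated and compared by log-rank test, unconditionally.

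A logistic regression for the influence of factors and a within-child paired t test complete the list.

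**The concern.** The decision rule and the analysis list do not meet. The rule needs one effect estimate with an interval, on the same scale as the margin. The list offers tests of difference, rates and percentages, and asks for no interval.

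The method also depends on the data. The t test hangs on a Shapiro-Wilk result. The move to rates hangs on whether any child is relapse-free or lost, which is close to certain: the plan expects 80% ever to relapse and 30% to have relapsed by 5.5 months. The default test is therefore very likely to give way to a comparison for which no test, interval or margin is given.

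The SAP states that the final analyses can be determined only after unblinding (SAP, Blinding). Any choice of method or horizon still open then would be made with allocation known. At stake is the trial's headline conclusion, which as written has no defined analysis behind it.

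**Working it through.** **1. The plan's own figure.** For a noninferiority comparison of means with no true difference, n per group = 2 × (SD/margin)² × (z_α + z_β)².

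- One-sided 0.05: 2 × (120/50)² × (1.645 + 0.842)² = 71.2, so 72. This matches the SAP.
- One-sided 0.025, which is what a two-sided 95% interval implies: 2 × (120/50)² × (1.960 + 0.842)² = 90.4, so 91.
- Power at 72 per group with the 95% interval: SE = 120 × √(2/72) = 20 days; Φ(50/20 − 1.96) = Φ(0.54) = 70.5%.

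**2. A difference test when the true loss equals the margin.** With a true loss of 50 days, SD 120 and 72 per group, a two-sided t test is significant with probability 70.5%, so it is non-significant in about 29.5% of trials. Simulation (10,000 trials) gave:

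- normal data: 30% (t test) and 32% (Mann-Whitney) non-significant;
- gamma data with means 185 and 135 days: 18% and 24%.

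In the gamma trials the 95% interval rule, applied in days, wrongly declared noninferiority in about 2.9%. With gamma times of mean 185 and SD 120, Shapiro-Wilk on 144 values was never passed in 2,000 runs, so under that shape the t test would hardly ever be reached.

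**3. Log-rank under an assumed constant hazard.** The input is 30% relapse at 5.5 months (SAP, Interim analysis): λ = −ln(0.70)/167.4 = 0.00213 per day.

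- Relapsed in the standard arm: 54.1% at 12 months and 78.9% at 24, so about 46% and 21% are relapse-free.
- At hazard ratio 1.5, 90.3% of the reduced arm has relapsed by 24 months. Events: 72 × (0.789 + 0.903) ≈ 122.
- z = ln(1.5) × √122 / 2 = 2.24; P(non-significant) = Φ(1.96 − 2.24) ≈ 39%.
- At hazard ratio 1.37 (about 120 events) the same steps give z = 1.73 and about 59%.

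**4. What happens if relapse-free children are left out.** Restricted mean to time T is (1 − e^(−λT))/λ. The mean among relapsers only is 1/λ − T·e^(−λT)/(1 − e^(−λT)). At hazard ratio 1.5:

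| Horizon | Restricted-mean loss | Loss among relapsers only |
|---|---|---|
| 12 months | 38 days | 11 days |
| 24 months | 88 days | 40 days |

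Only the 24-month row crosses 50 days. These are point values; the rule would also need the interval to clear the margin.

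**5. What 50 days means on each scale.**

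- Means of 135 and 185 days: ratio 185/135 = 1.37.
- 12-month restricted mean: the standard arm has 253.7 days. At hazard ratio 1.68 the reduced arm has about 203.7, a loss of 50. At hazard ratio 1.37 the loss is only 29 days.

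**6. Power for a restricted-mean rule at 72 per group, two-sided 95% interval, no true difference.**

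- 12 months, SD about 128: SE = 128 × √(2/72) = 21.3; Φ(50/21.3 − 1.96) ≈ 65%.
- 24 months, SD about 257: SE = 42.8; Φ(50/42.8 − 1.96) ≈ 21%.

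**The case against.** The best defence is that the SAP does contain a noninferiority criterion and does recognise censoring. Both are true, and they rule out several stronger readings.

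- A reader might infer that relapse-free children are dropped. The SAP never says so. It calls the outcome censored, uses data up to loss to follow-up, and lists Kaplan-Meier with log-rank unconditionally. Mann-Whitney could also rank children relapse-free at 24 months as tied, although it cannot properly place those lost earlier. The relapsers-only figures show what an unspecified choice could do, not what is planned.
- A reader might infer that only the t test can give an interval in days. That is wrong: inverting the Mann-Whitney test gives a shift with an interval, and Kaplan-Meier gives medians and means in days. The defect is that no such interval is requested.
- A reader might infer that a non-significant result will be taken as noninferiority. The SAP does not say this, and its stated rule requires an interval.
- A reader might infer that the open sign lets a clearly inferior schedule pass. The interim sections make earlier relapse on the reduced schedule the concern, so the rule reads sensibly as standard minus reduced. Stating the direction is a clarification.

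The constant-hazard model is also imperfect. It gives 254 days (SD 128) as a restricted mean, or 159 days (SD 104) among relapsers, not the planned 185 and 120. These objections narrow the point, but none supplies the missing estimate.

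**Conclusion.** The point holds and should be settled before unblinding. Following the primary analysis section as written does not yield the quantity that the decision rule needs, and the section names neither a deciding analysis nor a deciding horizon. This is more than missing detail, because the SAP specifies the primary analysis itself.

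That difference tests are no substitute follows from the plan's own margin, SD and sample size: about 30% are non-significant at a true loss of 50 days. The log-rank figure of about 39% at hazard ratio 1.5 rests on the assumed constant hazard and 24 months of complete follow-up. The contrast of 88 with about 40 days rests on that model and on an exclusion that the plan neither states nor rules out.

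**What to change.** Name one primary estimate at one horizon that uses censored data and does not depend on a normality test or on who has relapsed. Two workable choices:

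- the difference in Kaplan-Meier restricted mean relapse-free time to 12 months, standard minus reduced, with its two-sided 95% interval and the upper limit compared with the margin;
- a Cox hazard ratio with its interval, against a margin converted to that scale in advance. This fits the Cox calculation mentioned in the sample size section.

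Justify the margin on the chosen scale. Carrying 50 days over to a 12-month restricted mean corresponds to a hazard ratio of about 1.68 under the assumed hazard, against 1.37 for means of 135 and 185 days, so it would tolerate a larger relative worsening without saying so. State the direction of subtraction. Remove the Shapiro-Wilk and person-time switches, and make the remaining comparisons and the other horizon secondary. The SAP's blind review before unblinding is a natural place for the amendment.

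The cost is SAP wording, a little programming and a restated power. With 72 per group and a two-sided 95% interval, power is about 70.5% at SD 120 and about 65% for the 12-month restricted mean, not 80%. At SD 120, 80% would need 91 per group.
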